4.6 MEDICATIONS THAT CAN BE USED OCCASIONALLY

Participants will be instructed to report the use of any medications to their Study Coordinators.

Headache medications: Aspirin, Tylenol, Nsaids (Motrin, Naprosyn):

Pain medications: same as listed above

Infections: antibiotics for short term

Sleep medications and sedatives: antihistamines, hydroxyzine, over the counter drugs

Cold and allergy medications: antihistamines with/without ephedrine or other beta adrenergics -- many of these are over the counter combinations that should be ok as long as they do not contain steroids.

Laxatives: Milk of Magnesia, senna and cascara -- only occasional use

Antidiarrheal: Lomotil, Kaopectate -- only occasional use

Cough medicines: Robitussin, Ny-Quil

TABLE OF CONTENTS

CHAPTER FIVE: Diet

5.0	DESCRIPTION OF DIET	4
5.0.1	Terms used in this chapter	4
5.1	GENERAL INSTRUCTIONS	5
5.1.1	Procurement of food	5
5.1.2	Specifications for food	5
	Figure 5.1.2.1 DELTA-2 Food Specifications	6
5.1.3	Food Procurement Directory	14
5.1.4	Calibration of Food Balances	17
	5.1.4.1 DELTA Calibration Form for Food Balances	18
5.2	WEIGHING FOODS	19
5.2.1	Weighing fat and cholesterol containing items	19
5.2.2	Weighing casserole items	19
5.2.3	Foods that can be weighed or measured by volume	20
5.2.4	Foods that can be weighed to +/- 1 gram	20
5.2.5	Portion Control Unit Packs	25
5.2.6	Bread Products	25
5.3	PREPARATION	26
5.3.1	Containers	26
5.3.2	Meat, Fish, Poultry	26
5.3.3	Fat Blends for Unit Foods	26
5.3.4	Canned Fruits and Frozen Vegetables	27
5.3.5	Instructions for Cooking Pasta	27
5.3.6	Instructions for Cooking Rice	28
5.3.7	Fresh Fruit	28
5.3.8	Batch Preparation	28
5.3.9	Sandwich spread w/egg yolk (W1 lunch)	29
5.3.10	Reconstitution of egg yolk from egg yolk powder	29
5.3.11	Reconstitution of egg white from egg white powder	29
5.4	DIET, MENU, AND CALORIE ASSIGNMENT	30
5.4.1	Run-in	30
5.4.2	Randomization	30
5.4.3	Menu cycles	30
5.4.4	Unit foods	30

5.4.5	Estimating Energy Requirements	30
5.4.6	Energy Adjustment	31
5.4.7	Adjusting calories in feeding periods 2 and 3	31
	Figure 5.4.7.1: DELTA Menu Schedule - Protocol 2	32
5.5	GUIDELINES FOR PARTICIPATION IN DELTA	40
5.5.1	Minnesota DELTA Participant Guidelines	40
5.6	FEEDING	42
5.6.1	Discretionary foods, beverages and seasonings	42
5.7	QUALITY CONTROL OF DIET	43
5.7.1	Training	43
5.7.2	Organization and security of records	43
5.7.3	Diet Documentation Forms	43
5.7.4	Labels and Masking Diet Assignment	45
5.7.5	Columbia	45

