1.0.2 Study Outcomes

1. The primary lipid and lipoprotein endpoints will be plasma concentrations of total cholesterol and triglycerides, low density lipoprotein cholesterol, low density lipoprotein size, high density lipoprotein cholesterol, and apoproteins B and A-I.
2. A second group of lipid and lipoprotein endpoints will include apo E genotypes, HDL subfractions lipoprotein (a) and very low density lipoprotein cholesterol.
3. The primary hemostatic endpoints will be factor VII and plasminogen activator inhibitor I, and beta thromboglobulin.
4. A second group of hemostatic factors may include fibrinogen and platelet aggregation by flow cytometry.
5. Fasting plasma insulin and glucose levels will also be primary endpoints.
6. Other secondary endpoints will include postprandial lipids, lipoproteins, insulin, and glucose levels.
7. Several ancillary studies may be carried out to test sub-hypotheses.

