31. a. Are you taking or have you ever taken estrogen? [Estrogen or female hormones for hot flashes or symptoms of menopause] YES NO

b. If YES to 31a, are you currently taking estrogen? YES NO

c. If NO to 31a, do you plan to start taking estrogen? YES NO

RESUME ASKING QUESTIONS OF ALL APPLICANTS.

Eligibility Visit 1

Form Code: EV1
Version B 5/10/94

32. How often do you take antacids? [Circle the letter preceding the response]
D Daily W Weekly O Occasionally N Never

33. How often do you take laxatives? [Circle the letter preceding the response]
D Daily W Weekly O Occasionally N Never

34. Within the past six months, have you taken any medications on a regular basis prescribed by a doctor? YES NO [Go to question 41.]

If YES, Specify doctor-prescribed medications, including oral contraceptives, one per line: [Enter names of medications with correct spellings.]

a. Medication	b. Reason for Taking Medication	c. Date When Stopped (mm/dd/yy)	d. Plan To Resume
35. _____	_____	_____	YES NO
36. _____	_____	_____	YES NO
37. _____	_____	_____	YES NO
38. _____	_____	_____	YES NO
39. _____	_____	_____	YES NO
40. _____	_____	_____	YES NO

[Applicant's doctor-prescribed medications must be confirmed at this time.]

41. a. Within the past six months, have you taken any self-prescribed medication or nutritional supplements on a regular basis? YES NO

If YES, please list self-prescribed medications or supplements, one per line: [Enter names of medications with correct spellings.]

b. _____ c. _____ d. _____

e. _____ f. _____ g. _____

42. If you are taking self-prescribed medications or supplements, would you be willing to discontinue use of the self-prescribed medication or supplement for the duration of this study? YES NO

If the answer to question 42 is YES, inform the Study Coordinator.

Eligibility Visit 1

Form Code: EV1
Version B 5/10/94

HEIGHT AND WEIGHT [SEE HEIGHT / WEIGHT CUTPOINT TABLES in the Forms Guide]

[Choose whether you will enter height/weight in customary units (ft-in/lb) or metric units (cm/kg). Only enter responses for questions 43-44 or 45-46.]

Customary Units

43. Height (without shoes) a. ft: _____ b. in: _____

44. a. Weight (without shoes) lbs: _____

b. Is the applicant's weight recorded in question 44a greater than the upper weight limit for applicant's height in the ht/wt table? YES NO

Metric Units

45. Height (without shoes) cm: _____

46. a. Weight (without shoes) kg: _____

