4.5 PARTICIPANT WEEKLY MONITORING

Figure 4.5.1

Instructions for Completing the Participant Weekly Monitoring Form

Note that questions 7-13 on this form are asked at the first weekly interview concerning the participant's activity during the previous week.

Data from this form will be entered into the data management system.

DELTA ID

Apply the pre-printed DELTA ID label or write in the 5-character ID number.

Monday's Date

Enter the current Monday's date which is usually the first day each week that a participant is interviewed. Enter the date as month/day/year using leading zeros to fill in all spaces.

Question 1: Personnel Code Number

Record the personnel code number assigned to the DELTA study staff for the person completing this form.

Questions 2-4: Blood Draw

These items are completed only during weeks 5, 6, and 7.

2. Circle the number of the Feeding Period.
3. Circle the number of the week into the Feeding Period.
4. Fill in the specific date of the blood draw. Enter the date as month/day/year using leading zeros to fill in all spaces.

Questions 5-6: Weight

The participant will be interviewed twice each week, usually on Monday and Thursday, to record weight and other vital information.

- 5a-d. Enter the date, weight, and current calorie level from the first weekly interview, usually on Monday. In 5a, enter the date as month/day/year using leading zeros to

fill in all spaces. In 5b or 5c, record the participant's current weight either in pounds (lbs) or kilograms (kg), respectively. Weigh the participant before the dinner meal, without shoes or coats. In 5d, circle the calorie level based on the body weight in 5b or 5c. The calorie level is adjusted such that the participant's weight does not vary 2.2 pounds (1 kg) or more than the target weight. (*Note to the Interviewer: For target weight, use the weight recorded on the first day of feeding period 1 or the first weekly weight recorded during the first week of feeding period 1.*)

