- 6a-d. Enter the date, weight, and circle the current calorie level from the second weekly interview, usually on Thursday. In 6a, enter the date as month/day/year using leading zeros to fill in all spaces. In 6b or 6c, record the participant's current weight either in pounds (lbs) or kilograms (kg), respectively. Weigh the participant before the dinner meal, without shoes or coats. In 6d, circle the calorie level based on the body weight in 6b or 6c. The calorie level is adjusted such that the participant's weight does not vary 2.2 pounds (1 kg) or more than the target weight. (*See previous note under question 5 denoting target weight.*)

Question 7: Exercise (Answered based on information from the week preceding the first weekly interview.)

In 7a, circle either YES or NO. If the response is NO, go to question 8. If the response is YES, continue with 7b and circle one letter only corresponding to the correct response. (*Note to interviewer: If 7a is answered YES, inform the Study Coordinator.*)

Questions 8-9: Medications

In 8a circle YES or NO. If 8a is answered NO go to question 9. If 8a is answered YES complete b-g listing the name(s) of the medications(s) and the total weekly amount(s) taken. Be sure to list the reason the participant took the medication.

In 9a circle YES or NO. If 9a is answered NO go to question 10. If 9a is answered YES complete b-e listing the name of the supplement(s) and the total weekly amounts(s) taken. (*Note to interviewer: If 8a or 9a is answered YES, inform the Study Coordinator.*)

Questions 10: Illness (*Answered based on information from the week preceding the first weekly interview.*)

10. Circle either YES or NO. If the response is NO, skip to question 12 to continue.

If the response is YES, describe the illness in the space provided, writing legibly and avoiding abbreviations. Also, proceed to answer question 11.

Question 11: Change in Eating as a Result of Illness

In 11a circle YES or NO. If 11 a is answered NO go to question 12. If 11 a is answered YES, describe the reasons in the spaces provided and complete b and c by circling YES or NO. (*Note to the interviewer: For 11b and 11c, any diet history or action would be taken by the Study Coordinator or other DELTA personnel trained to do so.*)

Question 12: Smokers Only *(Answered based on information from the week preceding the first weekly interview.)*

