In 12a, circle either YES or NO. A change in smoking habits is defined as started smoking, stopped smoking, or increased or decreased smoking by at least 50 percent. If the response to 12a is NO, go to question 13. If the response to 12a is YES, then proceed with 12b and circle one letter only corresponding to the correct response. *(Note to interviewer: If 12a is answered YES, inform the Study Coordinator.)*

Question 13: Women Only *(Answered based on information from the week preceding the first weekly interview.)*

In 13a, circle either YES or NO. If the response to 13a is YES, then proceed with 13b and 13c, recording the date and circling the day of the week the participant began menstruating. *(Note to interviewer: This question should be skipped completely for men participants as well as for clearly postmenopausal women participants. NA is not needed as a response.)*

Reminder to All Study Personnel: Be sure to complete this form for each participant at the time of the last blood draw of the feeding period.

Participant Weekly Monitoring

Form Code: PWM
Version B 5/10/94

DELTA ID: _____

Monday's DATE: ____/____/____
[THIS WEEK] (mm/dd/yy)

1. Code Number of personnel completing this form: _____

BLOOD DRAW

[Complete numbers 2-4 during weeks 5, 6, 7.]

2. Period 1 2 3 [Circle correct number]

3. Week 5 6 7 [Circle correct number]

4. Date of blood draw ____/____/____
mm/dd/yy

WEIGHT [THIS week]

[Participants are weighed before dinner, without shoes or coats.]

5. a. Date of first weekly weight: _____
(mm/dd/yy)

First weekly weight, either in lbs or kg:

b. lbs: _____ or c. kg: _____

d. Current calorie level: 1500 2000 2500 3000 3500 [Circle correct number]

6. a. Date of second weekly weight: _____
(mm/dd/yy)

Second weekly weight, either in lbs or kg:

b. lbs: _____ or c. kg: _____

d. Current calorie level: 1500 2000 2500 3000 3500 [Circle correct number]

Be sure to administer this form at the last blood draw of the period!

Figure 4.5.2: Participant Weekly Monitoring

Participant Weekly Monitoring

Form Code: PWM
Version B 5/10/94

[Interviewer: Ask the participant the rest of the questions based on their activities during the past week.]

EXERCISE [Exercise is recorded at the first weekly visit following the weekend.]

7. a. In the past week, has your exercise level changed? YES NO [If NO go to question 8]
b. If YES, how has your exercise level changed: [Circle letter preceding your selection]

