Tube 4, identified as a Diatube, is a 5-ml blue top tube with a red label. It contains special stabilizers. It should be kept cold prior to the blood draw. It is recommended that it be chilled on ice at least 15 min before use. This tube will be collected on weeks 5 and 6 only. It must be placed on ice immediately after collection. The plasma from this tube is filtered and the filtered plasma is will be used for measurement of beta-thromboglobulin. These tubes may be purchased from the University of Vermont ([name]) or directly from American Bioproducts Company ([name]; Ph. [contact])

Tube 5 is a 7.0 ml purple stopper tube. This tube requires mixing after filling and placement on ice. After centrifugation, plasma is aliquotted into yellow-coded cryovials (0.5 ml). The plasma will be used for ancillary and supplemental studies.

Each draw tube is assigned a color-coated aliquot system. There is one type of aliquot used: 0.5 ml cryovials. The cryovials have colored caps.

4. Priority of tubes.

A total of approximately 41 ml will be drawn from each participant in five tubes at each endpoint package. The tubes are drawn in priority order.

The tubes are numbered 1-6. 1-2 and 6 are in a room temperature rack. Tubes 3, and 5 are kept on ice.

5. Forms.

a. Purpose:

The purpose of the blood collection form is to facilitate the collection of plasma and serum samples from participants. This collection must be done in a rapid and efficient manner, with maximum protection for the participant. In addition, the process must facilitate the monitoring of phlebotomy and other quality assurance parameters as well.

Note: All forms are to be completed in ink.

b. Description:

There are two parts of the Phlebotomy Processing Form associated with blood drawing. The top half is the participant/phlebotomy question about fasting status. If the person has eaten less than eight hours earlier, he/she should be rescheduled on an alternate day, within three days of the initially scheduled date.

The bottom half deals with phlebotomy and processing of samples.

These forms have the following purposes: 1) Assure the most efficient and safest possible venipuncture for participants. 2) Allow the monitoring of the quality of the above procedures. 3) Allow more efficient processing of the samples at central laboratories. 4) Provide information critical to the interpretation of assay results.

III. PROCESSING THE BLOOD SAMPLES

A. General:

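### Aspirin and NSAIDs are allowed with no preference for Tylenol before a draw, and the forms shown cannot place a draw-week dose before or after the beta-thromboglobulin draw (minor, precision only)

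*Protocol*

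**What the plan says.** - **Permission.** Section 4.6 opens its list with "Headache medications: Aspirin, Tylenol, Nsaids (Motrin, Naprosyn" and gives the same choices for pain. Participants must report any medication to the Study Coordinator. The section states no order of preference and no condition before a blood draw.
- **Endpoint.** Section 1.0.2: "The primary hemostatic endpoints will be factor VII and plasminogen activator inhibitor I, and beta thromboglobulin". On the tube for beta-thromboglobulin, Chapter 8, Section II.B.3 says "This tube will be collected on weeks 5 and 6 only".
- **Screening.** Question 41 of the Eligibility Visit 1 form asks "have you taken any self-prescribed medication or nutritional supplements on a regular basis", over the past six months. Question 42 then asks such users "would you be willing to discontinue use of the self-prescribed medication or supplement for the duration of this study".
- **Weekly recording.** The Section 4.5 instructions for item 8 read "If 8a is answered YES complete b-g listing the name(s) of the medications(s) and the total weekly amount(s) taken", and the reason for use is also taken. The data are keyed. On timing: "Note that questions 7-13 on this form are asked at the first weekly interview", and they refer to the week before. For the end of a feeding period there is a reminder: "Be sure to complete this form for each participant at the time of the last blood draw of the feeding period".
- **Draw day.** The Phlebotomy Processing Form (Chapter 8, Appendix II) asks for hours since food and hours since alcohol. It has no medication item.

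**The concern.** Beta-thromboglobulin is measured twice per diet and its tube is handled with special care: pre-chilling, stabilizers, immediate ice and filtration. Alcohol is barred for 48 hours before a draw (Section 5.6.1) and checked at the draw. Analgesics get neither a rule nor a check, although Tylenol stands on the same line as aspirin and the NSAIDs. If aspirin or an NSAID shifts the marker, an unplaced dose adds noise to a primary endpoint. The order of dose and draw is a data-collection field. An analysis plan can use the weekly flag, but it cannot recover an order that nobody recorded.

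**Working it through.** **1. What can be reconstructed from the forms shown**

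- Dose in the week before a draw week: reported on the draw week's form, so it is known to precede the draw.
- Dose in draw week 5 or 6: reported at the first interview of the following week, as a weekly total without a date. The draw date is recorded (item 4), but there is no dose date to set against it.
- Dose in week 7: the form repeated at the last draw covers the past week, so the order is largely settled. That draw carries platelet flow cytometry and no beta-thromboglobulin tube.

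The gap is therefore confined to doses in the draw week itself, for the week-5 and week-6 draws.

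**2. Inputs**

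The protocol gives no usage rate, drug effect, SD or power for beta-thromboglobulin, so there is no stated figure to reproduce. Assumed, with ranges:

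- *f*, share of draws with an undated draw-week dose: 5% to 20%.
- *q*, share of those doses taken before the draw: 0.5, the worst case.
- *d*, shift caused by a dose, in within-person SDs of one draw: 0, 0.5, 1 and 2.

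Exposure is taken as independent from draw to draw and unrelated to diet.

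**3. Cost of the missing order**

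Once the analysis adjusts for the weekly flag, the remaining uncertainty is whether a flagged dose came before the draw. Per-draw variance is multiplied by 1 + *f q*(1 − *q*)*d*², and the standard error by its square root. With *q* = 0.5:

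| *f* | *d* = 0 | *d* = 0.5 | *d* = 1 | *d* = 2 |
|---|---|---|---|---|
| 5% | 1 | √1.003125 = 1.0016 | √1.0125 = 1.0062 | √1.05 = 1.0247 |
| 20% | 1 | √1.0125 = 1.0062 | √1.05 = 1.0247 | √1.20 = 1.0954 |

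For *d* of 0.5 to 1 the standard error rises by 0.2% to 2.5%. A simulation of 2 million draws at *q* = 0.5 agreed within 0.1 percentage point.

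The result is sensitive to *q*. At *q* = 0.2 and *f* = 20% the factors are √1.008 = 1.004, √1.032 = 1.016 and √1.128 = 1.062. If a center drew blood on the day of the first interview, nearly all doses on the next form would follow the draw and the cost would be close to zero. The text shown does not fix the draw weekday.

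**4. In terms of power**

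For a two-sided 5% test with nominal 80% power, power becomes Φ((1.960 + 0.842)/factor − 1.960). A factor of 1.0016 gives 79.9%, and 1.0247 gives 78.1%.

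**5. Share of the data**

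One affected draw is half of that participant's beta-thromboglobulin values on that diet. With about 100 participants (Section 2.0, Table 1) and two draws each, it is 1 of about 200 values for the diet.

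**The case against.** The strongest reply is that nothing in the protocol conflicts. Occasional use is allowed on purpose, reported to the coordinator and keyed every week. Any medication named at telephone screening goes to medical review, and regular users of self-prescribed products are asked whether they would stop. Participants are seen at meals every weekday, and the data system lets staff attach a note to a field, so a date could be written down, although none is required. The harm depends on a drug effect that the documents never assert. The draw weekday is not stated, so *q* = 0.5 is itself a guess. A preference for Tylenol may also sit in material not shown: the participant agreements, the centers' own written instructions (Section 5.5 shows only Minnesota's, as an example), the Forms Guide or the laboratory training video.

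All of this stands as a limit on importance. It does not remove the gap in the forms shown.

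Three stronger readings are tempting, and the documents support none of them.

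- **Bias.** A reader might infer that permitting aspirin biases the diet comparison. Diet sequences are randomized (Section 5.4.2), participants are masked (Section 5.7.4), and a shift common to all diets cancels in the contrast. That use does not depend on diet is an assumption, but nothing in the text suggests otherwise.
- **Large loss of precision.** If use were ignored altogether, the factor would be √(1 + *p*(1 − *p*)*d*²), where *p* is the share of draws with recent use. With *p* = 20% and *d* = 2 that is √1.64 = 1.28. This supposes that the recorded weekly data go unused, so it does not follow from the missing date.
- **Distorted drug effect.** Adjusting for the weekly flag would estimate only *q* times the drug effect. The trial compares diets, and the drug effect is not a quantity it sets out to estimate.

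**Conclusion.** The point holds as a minor matter of precision. Section 4.6 states no preference before draws, and the forms shown do not order a draw-week dose against the week-5 or week-6 beta-thromboglobulin draw. The cost in the standard error of a diet contrast is about 0.2-2.5% for *d* of 0.5 to 1 with 5-20% of draws affected. It is larger only for a shift as big as 2 SD, and nil if the drugs do not move the marker. The usage rate, the drug effect and the timing split are all assumptions. The change is worth making because it is cheap and the order cannot be recovered later, but it is optional and the trial does not depend on it.

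**What to change.** 1. **Section 4.6.** Add a sentence asking participants to prefer Tylenol, already permitted, in a window before the week 5, 6 and 7 draws. The Laboratory Subcommittee and the Medical Officers set its length. A participant who needs aspirin or an NSAID takes it and is still drawn.
2. **Phlebotomy Processing Form.** Beside the alcohol item, add: date of last aspirin or NSAID, and product.
3. **Use of the item.** Flag beta-thromboglobulin and platelet values that fall inside the window, for a sensitivity analysis only. No draw is cancelled and no value discarded.

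The cost is one sentence, one form item and a small burden on participants before nine draws (three per diet, three diets). Dating an exposure is practicable, since item 13b of the weekly form already does so for menstruation. The 48-hour alcohol rule and its draw-day question provide the model. First check whether the center instructions, participant agreements, Forms Guide or training video already cover it.

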5.0 DESCRIPTION OF DIET

Three experimental diets will be used to test the hypotheses presented in Protocol 2. The nutrient specifications are as follows:

	Average American Diet	High Mono Diet	New Step One Diet
	Diet "D"	Diet "E"	Diet F"
Total fat, % Kcal	37	37	30
SFA, % Kcal	16	8	8
MFA, % Kcal	14	22	15
PFA, % Kcal	7	7	7
Fiber g/1000 Kcal	7.5	7.5	15
Simple CHO, % of CHO	40	40	*
Cholesterol	300	300	300
*Kept at same absolute level as "D" and "E" but with increased starch			

Diet D, the Average American Diet, was representative of the U.S. diet during the collection of NHANES II data from 1976 to 1980. (The newly released NHANES III data indicate that total fat and saturated fat intake have decreased to 34% and 13% of calories, respectively). The average American Diet, Diet A, was one of the experimental diets used in Protocol 1. Thus, it will be possible to examine the lipid/lipoprotein and hemostatic responses to an Average American Diet in an insulin resistant population and a healthy population studied previously.

Diet E is high in MFA and low in SFA. (It was designed to meet the lower range of the SFA recommendations of the Step-One Diet of the National Cholesterol Education Program Adult Treatment Panel-II Report). Because of the enrichment of this diet in MFA, the total fat content of Diet E is the same as that for Diet D.

Diet F meets the nutrient specifications of the Step-One Diet. Diets E and F differ in the amount of MFA and, therefore, total fat; the contribution of SFA and PFA to the diets is the same. Diet F is higher in dietary fiber and complex carbohydrates.

All experimental diets provide 300 mg of cholesterol per day to enable comparisons to be made between diets on the basis of differences in only the amount of MFA, complex carbohydrate and dietary fiber. The design of the experimental diets will answer the question of whether diet E or F is preferable for individuals who are insulin resistant. Since total fat and MFA are lower, and dietary fiber and the proportion of complex to simple carbohydrate are both higher in Diet F, versus Diet E, it will not be possible to identify the dietary factor that accounts for this. Rather, the diet design will permit comparisons between two different dietary patterns that both meet the ATP-II recommendations for SFA and cholesterol (e.g., a high complex carbohydrate, high fiber and lower fat diet versus a high fat and high MFA diet).

